13.1 Definition of Analysis Group

The data obtained from the subjects through this clinical trial will be divided into the Safety Set, FA (Full Analysis) Set. Statistical analysis will be performed by dividing it into PP (Per Protocol) Sets. The main population of this trial will be the PP Set, the secondary evaluation group will be the FA Set, and the safety evaluation will be analyzed with the Safety Set.

Full Analysis Set (FA Set)

Subjects who have been applied to an investigational device at least once after randomization and who can obtain information about the results of the primary efficacy evaluation after baseline are eligible.

Per-Protocol Set (PP Set)

The PP Set is for subjects included in the FA Set who have completed the clinical trial according to the clinical trial protocol without any serious protocol violations, and subjects who fall under the following cases will be excluded from the PP Set.

- 1) Dropout
- 2) Violation of Inclusion/Exclusion Criteria
- 3) Taking prohibited drugs or using prohibited treatments (except for other purposes)
- 4) Other cases that may be considered serious violations of the plan

Safety Set

Subjects who have been applied to an investigational device at least once after randomization and whose safety-related data have been evaluated at least once will be included.

13.2 General principles

Continuous variables present the number of observed subjects, mean, standard deviation, median, minimum, and maximum values, while categorical variables present frequency and percentage. Unless otherwise specified, all tests will be two-tailed tests at the significance level of 5%. All p-values will be presented up to 4 decimal places, and if they are less than 0.05, they will be judged to be statistically significant. The missing values that occurred in this clinical trial will be reflected in the analysis as they are without correction.

13.3 Subject Basis Information

Demographic data and basic characteristics will be summarized for each administration group, and will be conducted for FA sets.

1) Demographic information and basic characteristics

Demographic data and basic characteristics are summarized by dosing group. Continuous variables present the number of observed subjects, mean, standard deviation, median, minimum, and maximum, while categorical variables present frequency and percentage. Comparisons between dosing groups will be analyzed by two sample t-test (Wilcoxon's rank sum test if the normality distribution assumption is not satisfied) for continuous variables and Pearson's chi-square test (Fisher's exact test if cells with an expected frequency of less than 5 exceed 20%).

2) Medical history and prior medications

Medical history will be standardized to System Organ Class (SOC) and Preferred Term (PT) according to the latest version of the Medical Dictionary for Regulatory Activities (MedDRA) for each administration group, and the frequency, percentage, and number of medical history will be presented. The prior drugs will be standardized into Anatomical main group (Level 1) and Therapeutic subgroup (Level 2) according to the latest version of the WHO-ATC (World Health Organization-Anatomical Therapeutic Chemical) Index (WHO-ATC) Index for each administration group, and the frequency and percentage of subjects and the number of drug cases will be presented.

13.5 Secondary Efficacy Evaluation Methods

1) Mean score on the 100-mm Visual Analogue Scale (VAS) for back pain in the test and control groups as assessed by subjects at baseline and at 3 and 6 weeks

: Descriptive statistics (number of observed subjects, mean, standard deviation, median, minimum, maximum) of the 100-mm Visual Analogue Scale (VAS) for back pain assessed by subjects at baseline and at 3rd and 6th weeks for each administration group will be presented and analyzed with two sample t-tests (Wilcoxon's rank sum test if the normality distribution assumption is not satisfied).

2) Mean score on the 100-mm Visual Analogue Scale (VAS) for leg pain in the test and control groups as assessed by subjects at baseline and at 3 and 6 weeks

: Descriptive statistics (number of observed subjects, mean, standard deviation, median, minimum, maximum) of the 100-mm Visual Analogue Scale (VAS) for leg pain assessed by subjects at baseline and 3 and 6 weeks for each administration group will be presented and analyzed by two sample t-tests (Wilcoxon's rank sum test if the normality distribution assumption is not satisfied).

3) Mean of the Oswestry Disability Index (ODI) for the limitation of daily living in the test and control groups as assessed by subjects at baseline and at 3 and 6 weeks

: Descriptive statistics (number of observed subjects, mean, standard deviation, median, minimum, maximum) of the Oswestry Disability Index (ODI) for the limitation of daily living assessed by subjects at baseline and at 3rd and 6th weeks for each administration group will be presented and analyzed by two sample t-test (Wilcoxon's rank sum test if the normality distribution assumption is not satisfied).

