1. QUICK INFORMATION

1.1 Protocol Summary

Official title		A Multicenter, Randomized, Subject/Rater-blinded, Active-controlled, Non-inferiority Confirmatory Trial to Compare the Anti-adhesion Efficacy and Safety of CollabARRIER® and Guardix-sol After Surgery for Herniated Disc or Lumbar Canal Stenosis			
Clinical trial sponsors		Dalim Tissen Co., Ltd.			
Clinical Trial Sites and Clinical Trial Director		Department of Neurosurgery, Eunpyeong St. Mary's Hospital, College of Medicine, The Catholic University of Korea Department of Neurosurgery, Seoul St. Mary's Hospital, College of Medicine, The Catholic University of Korea Department of Neurosurgery, St. Vincent's Hospital, College of Medicine, The Catholic University of Korea Department of Neurosurgery, Asan Medical Center, Seoul Department of Neurosurgery, Korea University Anam Hospital, Korea University College of Medicine, Seoul, Korea Department of Neurosurgery, Ajou University Hospital			
Duration of the trial		Approximately 36 months from the date of approval of the clinical trial plan			
Clinical trial objectives		In order to prove that it is non-inferior by comparing the anti-adhesion effect and safety of postoperative adhesions caused by disc herniation or lumbar stenosis by comparing the investigational device CollabARRIER® and the control device Guardix-sol.			
Clinical trial design		A Multicenter, Randomized, Subject/Evaluator-Blinded, Active-Controlled, Non-inferiority Confirmatory Trial			
Subjects	Number of subjects	Total number of subjects: 69 (Initially, the target number of subjects was calculated to be 68 considering a dropout rate of 10%, but one additional person was enrolled during the recruitment process.)			
		Test group	Control group	Total Number of subjects	
		Number of subjects	30	30	
		Number of subjects considered for dropout 10%	34	34	
				68	

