s	Efficacy endpoints	Primary efficacy variables	
Descriptive statistics (number of observed subjects, mean, standard deviation, median, minimum, maximum) for MRI Scar score assessed by an independent Evaluator at 6 weeks for each dosing group are presented, and two-sided 95% confidence intervals are presented for the mean difference between dosing groups (test group-control group).

		Secondary efficacy variables	
Descriptive statistics (number of observed subjects, mean, standard deviation, median, minimum, maximum) are presented for the following endpoints and analyzed by two sample t-test (Wilcoxon's rank sum test if the normality distribution assumption is not satisfied).
 
 1) Mean score on the 100-mm Visual Analog Scale (VAS) for back pain in the test and control groups as assessed by subjects at baseline and at 3 and 6 weeks 2) Mean score on the 100-mm Visual Analog Scale (VAS) for leg pain in the test and control groups as assessed by subjects at baseline and at 3 and 6 weeks 3) Mean score on the Oswestry Disability Index (ODI) for the functional disability in the test and control groups as assessed by subjects at baseline and at 3 and 6 weeks

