9.2 Randomization Method

The randomization table will be prepared by a statistician who is not directly related to this clinical trial using SAS® (Version 9.4 or higher, SAS institute, Cary, NC, USA) so that each group can be assigned in a 1:1 ratio by stratified block randomization method considering the site as a stratification factor. Subsequently, subjects who participate in the clinical trial and meet the Inclusion/exclusion criteria will be sequentially assigned to each application group according to the randomization number, and the randomization number will be used as the subject identification code during the clinical trial.

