9.5.2 Blinding

This clinical trial was designed with subject and independent evaluator blinding. Since the two medical devices used in this clinical trial do not have an application and removal procedure in the subject's perceived situation, it is expected that a blinding design will be allowed, so this method was adopted. Since the investigator will know the treatment group assigned in advance by the application of the investigational device, blinding of the investigator is not allowed. However, this clinical trial is a controlled clinical trial, and in order to prevent bias in the primary efficacy endpoint, three radiology specialists were assigned as independent evaluators to maintain blinding during the evaluation of the primary endpoint. Attachment 7. Independent Evaluation Manual'.

The unique assignment code will be managed in a sealed state by the sponsor and the principal investigator of the clinical trial site, and the subject and investigator shall remain blinded to each subject's treatment arm assignment after the end of the study until the data management process is completed and the assignment code is released. If it is deemed necessary to release the subject's assignment code due to the occurrence of an emergency such as a serious adverse event, or if it is determined that it is absolutely necessary for the rights and safety of the subject, the blinding may be lifted according to the unblinding procedure.

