The investigator creates a folder for each subject and keeps the photo file. In the created folder, the photographs are stored in the form shown in the table below, separating the subject's visit time and the test group and control group. If the investigator saves each photo in the form of an electronic file on an external hard drive or USB, the monitoring personnel of the clinical trial site can create a material receipt sheet and send it to the independent data manager. Photographs should be sent at least once a quarter, and may not be sent if there are no registered patients. Photographs should be sent in a compressed folder if necessary, and the folder name should be the same. For details related to the evaluation procedure of independent evaluators, please refer to 'Attachment 7: Independent Evaluation Manual'.

Subject RX-NN photo folder name	Protocol No_Subject Number
Example Photo Folder Name of Subject R1-001	DRT-04_R1-001
Photographic name for subject identification	Protocol No_Subject Number_Visit Date_Placement Group
Example of test group photo name of V4 subject R1-001	DRT-04_R1-001_V4_Test Group

10.4.11 100 mm Visual Analogue Scale(VAS)

At the preoperative time point (baseline) and at 3 and 6 weeks after the application of the investigational device, subjects will come to the hospital for efficacy evaluation and undergo a 100 mm Visual Analogue Scale (VAS) Evaluation for back and leg pain. In the case of legs, VAS evaluation will be performed only on one of the two legs with severe pain. The 100 mm VAS marks the left end as no pain '0' and the right end as '100' for severe pain on a 100 mm parallel line. The subject draws a vertical line exactly on the parallel line and measures the mm from no pain (0) to the vertical line to

check the value. For details, refer to 'Annex 3. 100 mm Visual Analogue Scale (VAS) Evaluation Sheet'.

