10.4.12 Oswestry Disability Index(ODI)

At the preoperative time point (baseline) and at 3 and 6 weeks after the application of the investigational device, subjects will come to the clinic for efficacy Evaluation and undergo an Oswestry Disability Index (ODI) Evaluation of the limitation of daily living. Subjects will be evaluated in 'Annex 4. The Oswestry Disability Index (ODI) questionnaire will be used to evaluate the 'Oswestry Disability Index (ODI)', and the scoring method of the questionnaire is as follows [19].

Oswestry Disability Index(ODI) Scoring Method	
The maximum score for each section within the questionnaire is '5 points', and the total score for all 9 sections combined is '45 points'. In each section, if you check phrase 1, the score for that question item is '0 points', and if you check the last phrase (phrase 6), the score is '5 points'. Once all 9 sections are completed, the score will be calculated as follows:	
Calculations:	
$[\text{Total score} / 5 \times \text{sections answered}] \times 100 = \underline{\hspace{2cm}} \%$	
Example (1): If all sections are checked and the total score is 16 $[16 (\text{Total Score}) / 5 \times 9] \times 100 = 35.6\%$	
Example (2): If one section is missing or not applied, and the total score is 16 $[16 (\text{Total Score}) / 5 \times 8] \times 100 = 40.0\%$	

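### Back VAS, leg VAS and ODI at weeks 3 and 6 are compared without the baseline score or the site stratum: a valid test, but one that may lose precision and is exposed to chance baseline imbalance

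*Combined protocol and SAP*

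**What the plan says.** Section 13.5 gives the same method for all three secondary outcomes. Back VAS is "assessed by subjects at baseline and at 3rd and 6th weeks for each administration group will be presented and analyzed with two sample t-tests", with a rank-sum test if normality fails, and leg VAS and ODI have parallel wording. The synopsis (1.1, secondary efficacy variables) agrees: "analyzed by two sample t-test (Wilcoxon's rank sum test if the normality distribution assumption is not satisfied".

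The data for an adjusted analysis are collected. Section 10.4.11 takes VAS "At the preoperative time point (baseline) and at 3 and 6 weeks after the application of the investigational device", and 10.4.12 has patients "undergo an Oswestry Disability Index (ODI) Evaluation of the limitation of daily living" at the same three times. Section 9.2 allocates 1:1 by a "stratified block randomization method considering the site as a stratification factor"; section 1.1 lists six sites.

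No other section adds a change score, a baseline covariate or a site term for these outcomes. The general principles in 13.2 do not, and the paired before/after tests in 13.6.2 are for safety variables only. Baseline is one of the time points tested in 13.5. Section 13.3 also tests baseline characteristics between arms: "Comparisons between dosing groups will be analyzed by two sample t-test".

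**The concern.** VAS and ODI are the only patient-reported efficacy outcomes beside an imaging primary endpoint. With about 30 evaluable patients per arm, the treatment difference will be estimated imprecisely. A preoperative score that predicts the postoperative score removes variance at no cost in data. Without it, the result in this one trial moves with whatever baseline gap chance produces, and a reader cannot separate that gap from a device effect unless adjustment was specified in advance.

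Site has a smaller role. If outcomes differ between sites, a test that ignores a stratification factor uses too large a variance and becomes conservative.

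Testing the baseline scores does not help. In the randomised population any baseline difference is due to chance, and a p-value does not show whether it matters for the follow-up comparison.

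**Working it through.** **The plan's own figure.** Sections 7.3 and 7.4 give 30 evaluable per arm for the primary endpoint (margin 0.57, SD 0.774, true difference 0, one-sided 0.025). The non-centrality is 0.57 / (0.774 × √(2/30)) = 2.852. On 58 degrees of freedom the non-central t power is 0.80086, as printed. 30/0.9 = 33.3, rounded up to 34 per arm, 68 in total. This reproduces, and it supplies the 30 per arm used below. The plan gives no SD, correlation, effect size or power for VAS or ODI.

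**Assumptions.** r from 0 to 0.6; VAS SD 20–25 mm, equal at baseline and follow-up.

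**Large-sample gain from baseline.** The variance is multiplied by 1 − r² and the interval width by √(1 − r²):
- r = 0.3: 0.91 and 0.954 (variance 9% lower, interval 5% narrower)
- r = 0.6: 0.64 and 0.800 (variance 36% lower, interval 20% narrower)

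**Net gain at this sample size.** ANCOVA here spends one degree of freedom on baseline and five on site beyond the intercept, leaving 52 instead of 58. Simulation: 60 patients; six sites with assumed shares of 30/20/15/15/10/10%; assumed blocks of 4; normal data; no site effect; 5000 runs per r. Mean interval width, ANCOVA relative to the raw t-test:

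| r | Ratio |
|---|---|
| 0 | 1.017 |
| 0.2 | 0.995 |
| 0.3 | 0.970 |
| 0.45 | 0.908 |
| 0.6 | 0.813 |

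Two-sided type I error was 0.046–0.051 (raw) and 0.049–0.052 (ANCOVA). Mean estimated differences were within 0.007 SD of zero for both.

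**In millimetres.** SE of a difference = SD × √(2/30) = 5.16 mm (SD 20) or 6.45 mm (SD 25). Raw half-width = 2.002 × SE = 10.3 or 12.9 mm. Applying the ratios gives 10.0 or 12.5 mm at r = 0.3, and 8.4 or 10.5 mm at r = 0.6.

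**Chance imbalance.** The baseline gap has the same SE, so a gap above 5 mm has probability 0.333 (SD 20) or 0.439 (SD 25). The shift in the raw follow-up difference is r × gap:
- 5 mm gap: 1.5 mm (r = 0.3) to 3.0 mm (r = 0.6)
- gap at its 95% limit, 1.96 × SE = 10.1 or 12.7 mm: 3.0–3.8 mm (r = 0.3) or 6.1–7.6 mm (r = 0.6)

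Given a gap at that limit, the two-sided false-positive rate of the raw test by normal theory is about 8% (r = 0.3), 13% (r = 0.5) or 16% (r = 0.6). Averaged over all randomisations it is 5%.

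**Site.** With no site effect the site terms only cost precision: at r = 0.3 the ratio is about 0.96 with baseline alone and 0.97 with site added. With an assumed site intraclass correlation (ICC) of 0.1, baseline plus site gives 0.928 at r = 0.3. In a separate simulation with six equal sites of 10, the raw test's type I error at that ICC was 0.040–0.043.

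**Change scores.** Their variance relative to raw scores is 2 − 2r: 1.4 at r = 0.3, 1.1 at 0.45, 1.0 at 0.5 and 0.8 at 0.6. Below r = 0.5 they are worse than raw scores.

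**The case against.** An unadjusted comparison of randomised arms is a legitimate choice, and these outcomes have no margin, power or success rule. The benefit is assumed: surgery lies between the two measurements, so r could be low, and at r = 0.3 with SD 20 mm the half-width moves only from 10.3 to 10.0 mm. All of this stands. It limits the point to an improvement.

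The benefit from site also needs an assumption. With no site effect the site terms cost about 1% in width; with an ICC of 0.1 they more than repay it. The documents settle neither case, but a small premium is reasonable for a factor used in the allocation.

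Four narrower objections also stand:
- Section 13.5 plans no confidence interval for VAS or ODI, so the narrowing refers to an interval that the plan should add.
- Unbiasedness and chance-only baseline differences hold for all randomised patients. The Full Analysis and Per-Protocol Sets in 13.1 are selected after randomisation, which is a separate question that ANCOVA does not answer.
- Some sites may be very small; under the assumed shares, two have six patients each.
- The simulation compares ANCOVA with the t-test on normal data. The gain over the planned rank-sum fallback was not estimated.

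**Conclusion.** The point holds as a recommended improvement. Sections 13.5 and 1.1 use neither baseline nor site for VAS and ODI, and nothing elsewhere supplies an adjusted analysis. The net effect at 60 evaluable patients runs from an interval 2% wider (r = 0) to 19% narrower (r = 0.6), with break-even near r = 0.2. These figures assume normal data, the stated site shares and block size, and no site effect. The potential loss is small and the potential gain moderate. The raw tests are not invalid, and neither the sample size nor the non-inferiority decision on the MRI scar score (13.4) changes. Confidence in the size of the gain is medium, because r and the SDs are not in the documents.

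**What to change.** In 13.5 and 1.1, analyse back VAS, leg VAS and ODI at week 3 and at week 6 by ANCOVA on the follow-up score, with treatment, baseline score and site as terms. Report the adjusted difference with its 95% confidence interval. State in advance how very small sites are pooled. Keep the rank-sum test as a sensitivity analysis if residuals are clearly non-normal. Do not substitute plain change scores. Present baseline scores descriptively in 13.5 without a test, and drop the baseline tests in 13.3.

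No new data are needed. Because section 13 is part of the protocol, the change is an amendment needing IRB or Ministry approval under 19.6. Timing matters: 1.1 reports 69 subjects and says "one additional person was enrolled during the recruitment process", so enrolment appears complete, and 9.5.2 acknowledges that the investigator knows the arm. The amendment must be dated before data lock and code release; 9.5.2 keeps assignments closed "until the data management process is completed and the assignment code is released". If that point has passed, keep the raw tests as planned and label the adjusted analysis post hoc.

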13.6 Safety Evaluation Methods

13.6.1 Adverse Events

The number of subjects, incidence, and number of occurrences are presented for adverse events (TEAEs), adverse medical device reactions (ADEs), and serious adverse events/adverse medical device reactions (Serious AEs/ADEs) that occurred after the application of the investigational device.

Adverse events, adverse medical device reactions, and serious adverse events are standardized with System Organ Class (SOC) and Preferred Term (PT) according to the latest version of the Medical Dictionary for Regulatory Activities (MedDRA), and the number of subjects, incidence, and number of adverse events are presented.

13.6.2 Laboratory tests, vital signs, physical examination

Laboratory tests, vital signs, and physical examination data will be analyzed with descriptive statistics (number of observed subjects, mean, standard deviation, median, minimum, maximum) if they are continuous data, and two sample t-tests (Wilcoxon's rank sum test if normality distribution assumptions are not satisfied). The comparison before and after the application of the investigational device will be analyzed by Paired t-test (Wilcoxon signed rank test if the normality distribution assumption is not satisfied).

Categorical data will be presented with frequencies and percentages and analyzed by Pearson's chi-square test (Fisher's exact test if cells with an expected frequency of less than 5 exceed 20%). The comparison before and after the application of the investigational device will be analyzed by McNemar's test.

13.6.3 Concomitant medications

Concomitant medications will be standardized based on the latest version of the WHO-ATC (World Health Organization – Anatomical Therapeutic Chemical) Index by Anatomical Main Group (Level 1) and Therapeutic Subgroup (Level 2), and the number of subjects, percentage, and number of medications will be presented for each treatment group.

14. EVALUATION CRITERIA, EVALUATION METHODS, AND REPORTING METHODS FOR SAFETY INCLUDING ADVERSE EVENTS

